Mattresses that have dual-functionality are excluded. This may be the ability to switch between static and alternating, such as Talley Quattro or Arjo Duo2; or mattresses that use combined static and alternating functionality, such as Curocell Cirrus or Talley Quattro Fusion. Although these mattresses may have clinical applicability in a community setting, their use during the study could confound results, particularly if they are not used as allocated, for example switched to alternating when the participant has been allocated to the static treatment group.

Cushions

To ensure that changes in pressure injuries are due to the mattress and not impacted by time spent sitting out of bed, all participants will be provided with the same air pressure cushion. Air cushions have been shown to have the lowest interface pressure, along with water cushions (Defloor & Grypdonck, 2000). As there are not many water cushions commercially available, an air cushion will be used (high profile ROHO cushion). These cushions are commonly prescribed for people at high risk of developing pressure injuries and so will be familiar to the treating clinicians should any trouble-shooting be required.

Wound Care

Wound care will be provided to the participants as per the current practice for Community Care Nursing, ACT Health. This includes the use of best-practice methods, such as Mepilex range as wound dressing with foam or cavity fillers as needed. Frequency of wound care days will vary depending on the stage of healing. Generally for Grade 2 wounds, wound care occurs every second day, reducing quickly to twice a week, then once per week. Once the wound reaches the stage of visits once per week the wound is considered almost healed as per the RevPWAT (score <2) and thus endpoint for the study.

Data Collection

Participants will be individually coded to prevent identification by assessors and by primary investigator when collecting survey data. Data will be kept in a limited-access folder on secure ACT Health servers behind ACT Health firewalls.

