Comparing wound healing times	Independent t-test (average healing time reactive surfaces vs average healing time active surfaces)			
Comparing number of new pressure injuries developed	Independent t-test (total number of new pressure injuries reactive surfaces vs total number of new pressure injuries active surfaces)			
Comparing number of pressure injuries not healed at 8 weeks	Independent t-test (number of pressure injuries not healed at 8 weeks for reactive surfaces vs active surfaces)			
Changes in Pain scores	2-way Mixed ANOVA – between group analysis to compare pre- and post-pain scores for each mattress type, independent group analysis to compare the mattress types			
Changes in time spent in bed	2-way Mixed ANOVA – between group analysis to compare pre- and post-time for each mattress type, independent group analysis to compare the mattress types			
Changes in frequency of repositioning	2-way Mixed ANOVA – between group analysis to compare pre- and post-frequencies for each mattress type, independent group analysis to compare the mattress types			

If the assumptions cannot be met, despite data transformation, then the relevant non-parametric tests will be completed (eg Mann-Whitney instead of Independent t-test).

Ethical Considerations

Ethics Approval

Ethics approval for this study will be sought from the ACT Health Human Research Ethics Committee and the University of Canberra Human Research Ethics Committee. As the design of the study reflects current practice, with all chosen mattresses being supplier-stated to be appropriate for Grade 2 pressure injuries, there will be minimal risk to participants for participating.

Data Management

During the data collection phase, data will be kept in restricted folders on ACT Health servers behind ACT Health firewalls so that all required parties will be able to access the data, negating the need for data to be emailed or transferred via USB. At the completion of the project the data will be de-identified and a copy provided to University of Canberra for archiving. This record is expected to be maintained for a minimum of seven years as per ACT Legislative requirements ("Health Records (Privacy and Access) Act 1997 (Republication No 27) (ACT)," 2016). Clinicians will continue to document in the clinical file as per current policy, including the allocated mattress.

Consent and cognitive impairment

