b) Provision of support surface will be based on availability.c) Mattress and cushion to be provided and set-up	Primary Researcher ELS Staff Primary Researcher OR ELS Staff
type and ROHO cushion b) Sales Representative to choose mattress from pre-determined list based on mattress type and storeroom availability c) Mattress and ROHO cushion to be provided and set-up	Primary Researcher Sales Representative Primary Researcher OR Sales Representative Primary Researcher
 mattress and cushion, including contact information 12. Wound Management: Wound Management as per standard practice with the following additions: Photograph to be taken as per study recommendations at every dressing change Review participant for changes in function, including skin check for new pressure injuries if new pressure injury has developed this should be photographed and referred to Wound Nurse Practitioner and Primary Researcher for review for ethical impact Repeat Waterlow weekly 	Community Nurses
13. Photograph Management: Photograph will be placed in ACT Health e-note template for photographs in a clinical file with unique identifier only (photograph enlarged for one photograph per page). Document to be saved in PATHFILE (Saved as: "Photograph [Unique identifier] — [date YYMMDD]"), where date is date photo was taken	Community Nurses
	Tissue Viability Nurses
 Data Entry Data from RevPWAT to be entered into data spreadsheet on a weekly basis by Research Team Data from hard-copy surveys will be entered into Qualtrics by Research Team as they are completed (to be entered within one week of survey) 	Primary Researcher Research Team/Admin Support Research Team/Admin Support Primary Researcher

Step	Who
 Participant Completion of study endpoints will be determined by one of the following: e one week following complete healing of the initial pressure injury as determined by the RevPWAT (ie at the point when Community Nursing would be leaving the dressing on for a week – PWAT score of 0 for all subscores except subscore 8, where a score of up to 2 can be permissable) e weeks following the provision of the mattress e removed from the allocated surface – for example by request, move areas, hospitalisation, death, significant deterioration of existing wounds (such as progression to a Grade 3 pressure injury or development of an unstageable pressure injury) 	Information only

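### New pressure injuries are compared as raw totals, although follow-up ends when the study wound heals, so a slower-healing arm is observed longer and shows more injuries at the same true rate

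*Protocol*

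**What the plan says.** Appendix A, step 12 (Wound Management), lists additions to standard wound care by the community nurses, among them: "Review participant for changes in function, including skin check for new pressure injuries". The skin check has no interval of its own. Only the Waterlow in that step is given a weekly interval.

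The Wound Care section under Intervention states "Frequency of wound care days will vary depending on the stage of healing" and adds: "Generally for Grade 2 wounds, wound care occurs every second day, reducing quickly to twice a week, then once per week".

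In Appendix A, participation ends at the earliest of three events: "one week following complete healing of the initial pressure injury as determined by the RevPWAT", a fixed number of weeks after mattress provision, or removal from the allocated surface. The number of weeks is not legible in the text available. The analysis table has a row "Comparing number of pressure injuries not healed at 8 weeks", so 8 weeks is taken as the maximum here. A final skin check is made at the end of participation.

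The Statistical Analysis table tests new injuries with an independent t-test described as "total number of new pressure injuries reactive surfaces vs total number of new pressure injuries active surfaces". No allowance for time observed is stated.

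**The concern.** A count of events needs a denominator when participants are observed for different lengths of time. Here the length of observation is set by healing of the study wound, which is the primary outcome. A participant who heals in two weeks can contribute new injuries for about three weeks, and one who does not heal can contribute for the full period. Check frequency also follows healing, because visits thin out as the wound improves.

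If one mattress heals wounds more slowly, its arm will tend to show more new injuries for that reason alone. The two results would then read as independent evidence pointing the same way, when one partly generates the other. This matters because the Adverse Event section makes new injuries a named event for referral, and the table row is the only planned comparison of them between mattresses.

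**Working it through.** The protocol gives no rate, margin or power for new injuries, so there is no figure of its own to reproduce.

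**Inputs from the protocol.** Follow-up stops at healing + 7 days or at the maximum (taken as 56 days). Visits run every 2 days, then twice weekly (3.5 days), then weekly. There is a final skin check. The target is 60 participants, 30 per arm.

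**Assumptions, not in the protocol.** Healing time is gamma with shape 2 and mean μ. The true rate is 0.05 new injuries per person-week in both arms. A new injury stays visible for an exponential time with mean 3, 7, 14 or 21 days. Visits are every 2 days for the first 40% of healing time, every 3.5 days until healing, then weekly.

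**Step 1: length of observation.** With θ = μ/2 and c = 56 − 7 = 49 days, mean follow-up in days is

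E = 7 + 2θ − exp(−c/θ)(2θ + c).

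- μ = 14: 7 + 14 − 0.00091 × 63 = 20.9 days (2.99 weeks)
- μ = 21: 7 + 21 − 0.00940 × 70 = 27.3 days (3.91 weeks)
- μ = 28: 7 + 28 − 0.03020 × 77 = 32.7 days (4.67 weeks)
- μ = 35: 7 + 35 − 0.06081 × 84 = 36.9 days (5.27 weeks)

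At equal true rates, the expected number of injuries that occur is proportional to follow-up. The slow/fast ratios are 32.7/27.3 = 1.20, 36.9/27.3 = 1.35 and 32.7/20.9 = 1.56.

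**Step 2: injuries found.** A simulation of 60,000 participants per arm, with the visit pattern and final check, gave these slow/fast ratios over the four injury durations:

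| Mean healing (days) | Raw total found | Due to follow-up length | Due to probability of detection |
|---|---|---|---|
| 21 v 28 | 1.19–1.24 | 1.19–1.20 | 1.01–1.02 |
| 21 v 35 | 1.35–1.40 | 1.34–1.35 | 1.01–1.04 |
| 14 v 28 | 1.57–1.66 | 1.56 | 1.01–1.07 |

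Simulation noise in the ratios is roughly 2–3%. Checks per week barely differ (2.28 v 2.38 for 21 v 28 days; 2.16 v 2.38 for 14 v 28), whereas total checks do (8.9 v 11.1; 6.5 v 11.1). With equal healing in both arms the ratio was 1.03, within noise of 1.

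**Step 3: what removes the excess.**

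- Weekly checks in both arms, raw totals, same stopping rule: still about 1.20 (21 v 28) and 1.52–1.56 (14 v 28). Equalising the checks alone does not help.
- All injuries found, divided by follow-up time: 1.00–1.06 across the scenarios in the table.
- Injuries found at weekly checks, divided by participant-weeks: 0.98–1.00.

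**Step 4: chance differences.** With μ = 21 the SD of healing time is 21/√2 = 14.8 days. The standard error of the difference in mean healing time, with 30 per arm, is 14.8 × √(2/30) = 3.8 days. A difference of several days can therefore arise without any mattress effect. Over repeated trials that is noise rather than bias, but in this one trial it would shift the raw totals in the same way.

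**The case against.** The strongest objection is that nothing goes wrong unless healing differs, and the protocol expects the mattresses to be equivalent. That is correct as far as it goes, but the trial exists to test that expectation, and the new-injury comparison should not depend on it.

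A second objection is that new injuries are not listed under Outcome Measures and that safety is handled case by case by the monitoring board. That limits the weight of the point. It does not repair a comparison that the analysis table fixes.

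A reader might infer that check frequency is the main problem. If an injury lasts a mean of m days and checks are d days apart, the chance of seeing it is (m/d)(1 − exp(−d/m)). For m = 3 this is 0.73, 0.59 and 0.39 at d = 2, 3.5 and 7; for m = 7 it is 0.87, 0.79 and 0.63. Every-second-day visits would then find 1.4 to 1.9 times as many injuries as weekly visits. Those ratios compare stages of care, not arms. Participants who heal pass through the stages in either arm, and the weekly stage is short: "Once the wound reaches the stage of visits once per week the wound is considered almost healed". It also closes with the final skin check. The durations of 3 and 7 days are assumptions, and longer ones shrink the effect. Nor is it stated outright that a skin check happens at every visit; that is read from its place in step 12.

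A reader might also infer that adjusting for time at risk would not help. Step 3 shows that it removes nearly all of the excess.

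**Conclusion.** The point holds for raw totals with healing-dependent follow-up. At equal true rates the slower-healing arm is expected to show about 1.2 to 1.6 times as many new injuries under mean healing times of 21 v 28 to 14 v 28 days. Longer observation accounts for almost all of it, and those extra injuries are real ones that occur in a longer window. Healing-driven check frequency contributes at most about 1.04 to 1.07, mainly for injuries lasting only a few days.

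The sizes rest on assumed healing times, injury durations and visit pattern, and on an 8-week maximum. The direction, and the dominance of follow-up length, held in every scenario with unequal healing. The documents do not support reading this as mainly a detection problem, or as a distortion that arises when the mattresses heal equally well.

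**What to change.** In the Statistical Analysis table, replace the t-test on total new injuries with a comparison of new injuries per participant-week on the allocated surface. A Poisson or negative binomial model with log follow-up time as offset would do. Count all new injuries found at any visit and at the final skin check.

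Add one sensitivity analysis that counts only injuries present at the weekly Waterlow visit and at the final check, again per participant-week. This removes the small remainder from healing-driven check frequency without discarding observed injuries from the main comparison.

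The cost is a changed table row, a flag for the weekly Waterlow visit, and slightly more analysis work. Follow-up time comes from the dates of mattress provision and end of participation. Checking and referral at every visit are unchanged. The rate model assumes a roughly constant rate over time on the mattress, which should be stated. Following everyone for a common 8 weeks with fixed weekly checks would also work (ratio 0.98–1.00 in the simulation), but it means extra visits after healing and is not needed for this purpose.

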It is likely that through coincidence there will be participants who do not have capacity to consent to participate. Potential participants will be screened for cognitive impairment and flagged for additional investigation via a cognitive screening assessment. This study is considered by ACT Legislation as 'low risk research' due to the fact it is comparing the effectiveness of two established standard treatments during routine health care (ACT Health Research Ethics and Governance Office, no date). As a result, if a cognitive impairment is determined then consent will be sought from the potential participant's (in priority order):

- person with enduring power of attorney;
- their guardian; or
- their health attorney, defined as a domestic partner, their carer or a close relative or friend (ACT Health Research Ethics and Governance Office, no date).

This is the most likely vulnerable population to be included in the study.

Adverse Event - Deterioration or development of new pressure injuries

All new pressure injuries and all deteriorating pressure injuries will be referred to the Data Safety and Monitoring Board (DSMB), consisting of Community Care Wound CNC, Community Care Wound Nurse Practitioner and Primary Investigator. This committee will review the circumstance to determine the cause of the deterioration or new pressure injury. If the suspected cause is something external to the mattress then the mattress may be able to remain in place. If no external cause can be found, then it is possible the mattress may have been a factor and the participant may need to leave the trial. This will also be the case should the pressure injury deteriorate to become a Stage 3, Stage 4, Suspected Deep Tissue Injury or Unstageable pressure injury.

Support surface provision during the study

Support surfaces being provided for the study are being supplied by one of two options:

- Equipment suppliers Astris Lifecare and Invacare (mattresses and cushions are being donated for the duration of the study, provided on a needs-basis).
- ACT Health Equipment Loan Service

Which service provides the support surfaces will depend on availability at the time and speed that delivery can occur. Agreements are being drawn up with Astris Lifecare and Invacare with regards to maintaining the privacy of participants and the intellectual property of the results, including the agreement that the results

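### Appendix A step 12 has nurses refer only new pressure injuries, to two people, whereas the main text sends new and deteriorating injuries to the three-member DSMB

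*Protocol*

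**What the plan says.** Main text, Ethical Considerations, adverse event section: "All new pressure injuries and all deteriorating pressure injuries will be referred to the Data Safety and Monitoring Board (DSMB", a board "consisting of Community Care Wound CNC, Community Care Wound Nurse Practitioner and Primary Investigator". Its task is stated next: "This committee will review the circumstance to determine the cause of the deterioration or new pressure injury". If an outside cause is suspected, the mattress may be able to stay. If none is found, "the participant may need to leave the trial". The section then extends this to progression: "This will also be the case should the pressure injury deteriorate to become a Stage 3, Stage 4", and it goes on to name suspected deep tissue injury and unstageable injury.

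Appendix A step 12, Wound Management, is assigned to the Community Nurses. It lists additions to standard practice. One is a photograph at every dressing change. Another is "Review participant for changes in function, including skin check for new pressure injuries", followed by the referral instruction: "if new pressure injury has developed this should be photographed and referred to Wound Nurse Practitioner and Primary Researcher for review for ethical impact".

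Appendix A, participant completion step, is marked as information only. Removal from the allocated surface is one way in which participation ends, and an example given is "significant deterioration of existing wounds (such as progression to a Grade 3 pressure injury or development of an unstageable pressure injury". That step does not mention DSMB review.

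The Intervention section of the main text points to Appendix A for the details of the study protocol.

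**The concern.** Appendix A is the text that field staff will work from. If its referral step is narrower than the safety rule in the main text, the reviewers see fewer events than the Protocol intends.

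The omitted event is a foreseeable one. Inclusion criteria 3 and 5 require an existing Grade 2 injury that the participant cannot reposition off, and step 9 gives the risk of the wound deteriorating as the reason for its two-day target for supplying the surface. The board's finding on cause bears on whether a participant stays on the allocated mattress. A case that never reaches the board therefore gets no such finding.

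**Working it through.** No arithmetic applies. The check is a side-by-side reading of the adverse event section and Appendix A.

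1. **Event referred.** Main text: two kinds, new injuries and deteriorating injuries, all of them. Step 12: one kind, new injuries. The skin check in step 12 is likewise directed at new injuries, and nothing in the step concerns worsening of the wound already under treatment.

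2. **Recipients.** Main text: the DSMB, with three members (Wound CNC, Wound Nurse Practitioner, Primary Investigator). Step 12: two people (Wound Nurse Practitioner, Primary Researcher). They correspond to two of the three members only if Primary Researcher and Primary Investigator are the same role, which the Protocol does not say. Step 12 names neither the DSMB nor the Wound CNC.

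3. **Purpose.** Main text: to find the cause of the injury or deterioration. Step 12: a review of ethical impact. These are different questions, and only the first bears on whether the mattress can stay.

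4. **Deterioration elsewhere in Appendix A.** It appears in the completion step as an example of removal from the surface. The examples given are marked worsening (Grade 3 or unstageable). No referral is attached, and a wound that worsens but remains Grade 2 is not addressed.

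5. **Link between progression and leaving.** The main text says that a participant whose injury progresses may need to leave. The completion step lists significant deterioration as an example of removal that ends participation. The first describes a judgement and the second an end state. Neither says how one leads to the other, or whether the board must review the case first.

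6. **Backstop.** The quarterly audit described under Study protocol audits covers consent forms, photograph and assessment documents, surveys and mattress provision. Adverse event referrals are not on that list, so the audit would not clearly reveal the gap.

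7. **Who is exposed.** The planned sample is 80, and all have a Grade 2 injury at entry. The Protocol gives no rate of deterioration, so this figure is the number at risk of the event and not an estimate of missed referrals.

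**The case against.** The strongest reply is that step 12 is silent on deterioration and does not countermand the main text. The adverse event section is current protocol text and still requires the referral. Step 12 lists additions to standard practice, so it is not a full account of what a nurse does about a worsening wound. All of this stands. A reader might infer from step 12 that a worsening study wound never triggers the review, and the documents do not support that. They support only that the nurses' step lacks the instruction.

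Second, the Appendix A step on assessing wound photographs, to which step 17 refers, cannot be read in the available text; only its assignment to the Tissue Viability Nurses survives. A trigger for deterioration there cannot be ruled out. This also stands and limits the conclusion to the readable text. It would not remove the conflict over recipients and purpose in step 12.

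Third, the two named people could be first contacts who then convene the board. That is possible, but the Protocol does not say so, and the stated purpose still differs.

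Three further inferences should be resisted:

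- The completion step does not name Stage 4 or suspected deep tissue injury. This is not a contradiction: its grades are given as examples, and Information Box 1 classes suspected deep tissue injury under unstageable.
- A reader might suppose that two nurses using the two texts would remove different participants. Neither text has nurses deciding removal: the main text makes it follow the board's review, and the completion step assigns it to no one.
- A reader might add that each removal costs a primary outcome. The gap is in referral, not removal; a missed referral would, if anything, lead to fewer removals, and an intention-to-treat analysis is planned beside the per-protocol one.

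**Conclusion.** The concern holds as an internal inconsistency in a participant-safety rule. Step 12 and the adverse event section differ on event (one kind against two), on recipients (two named people against a three-member board) and on purpose (ethical impact against cause). In the readable text, a nurse following only step 12 could leave deterioration of the existing study wound unreferred, especially short of Grade 3. The unstated link between progression, board review and ending participation is a secondary point.

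The conclusion assumes that nurses work from Appendix A, as the main text's pointer to it suggests. It also assumes that the unreadable photograph-assessment step contains no equivalent trigger; if it does, the gap on deterioration narrows, but the differences in recipients and purpose remain. The effect on the number of referrals cannot be sized from the Protocol.

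**What to change.** Reconcile the adverse event section with Appendix A (step 12 and the participant completion step) so that both give:

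- the same list of events to be referred;
- the same recipients, stating whether the Primary Researcher and the Primary Investigator are one role and whether the people named in step 12 are first contacts for the DSMB or replace it;
- the same purpose of the review;
- how progression of an injury relates to ending participation, and whether board review comes first.

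Carry the reconciled trigger into step 12, since that is where the nurses will look, and check the photograph-assessment step against it. Which referral and continuation rule applies is for the sponsor to decide. The cost is a few lines in the two places. No extra visits are needed, because the nurses already photograph the wound at every dressing change.
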